Assessments will be completed primarily at the IU Health Neuroscience Center by trained assessors, but can be broken down into multiple shorter visits or completed in part by phone, if desired. [During the COVID-19 health crisis, all study visits will be completed by phone or Zoom.] Participants completing all baseline assessments will be randomized. Randomization will be stratified by age (60-69; 70 and over) and MRI completion. To address frequent moves and service changes in the population, we will obtain contact information for 2 relatives/friends at enrollment.

[figure not shown]
[After the IU Research Restart beginning June 1 2020, study visits will be completed by a combination of in-person and telephone measures until full in-person measures are allowed to resume. Biospecimen collection, imaging, and Viromeaging substudy enrollment will be included; written consent will be required.]

Interventions. As noted, a professional UX design team led a user-centered design research effort to integrate the speed of processing and MIND food interventions. First, five users evaluated application screens and functions rendered on Sketch (https://www.sketchapp.com/). Second, these same users experienced

tablet-operated, interactive prototypes created through an application called Axure (http://www.axure.com/). Third, the design was evaluated by an outside expert team including human factors and software engineers and design researchers. Finally, the MindSpeed app was evaluated in a different group of five users for one week (ages 52-76yrs). The pilot study involved a combination of interview sessions, iterative design and usability evaluation of the prototype, food delivery and reporting, and game play (BrainHQ). Some older adults with low education have limited reading skills, low computer familiarity, and limited eyesight. Thus, a major objective of the design work was to make the application easy for the target group to use. This appears to have been achieved. First time users reported "this is self-explanatory" and "I will know how to use after first time, pretty simple." Findings from the pilot indicate that participants will shop through the app, accept home delivered foods, play speed training games, and track incentives.

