In order to test the mediating effect of blood biomarkers, brain structure, and brain function variables we need to establish the association between the mediating variable and primary outcome, after controlling for the intervention effect. Such an association is evaluated using a partial correlation. With our sample size, we have more than 80% power at the 0.05 alpha level to test a partial correlation of 0.3 between mediating variables and the primary memory composite outcome. Effect modifiers include adherence, percent body fat, age, baseline cognitive status, comorbidity, and *APOE* ε 4 carrier status. Evaluation of moderating effects is an exploratory aim and detection of such effects requires large sample sizes. Our study is therefore only able to explore treatment moderators. In addition, our sample size provides accuracy with no more than 8% margin of error at the 95% confidence level for feasibility outcomes.

Analytic Plan: *Preliminary Analyses.* Baseline characteristics of participants will be compared across treatment arms. We will also compare the baseline scores on outcome measures across treatment arms. For continuous variables, means and standard deviations will be reported. Frequency tables will be reported for categorical variables. Normality of continuous outcomes will be examined using a normal probability plot. For highly skewed measurements, appropriate transformations will be applied to achieve approximate normality. Repeated measurements over time will be graphed as spaghetti plots and examined for outliers. All data will be examined for completeness. The baseline characteristics will be compared across treatment arms and between participants who do and do not complete the study. If any significant differences exist, we will control for differences in the subsequent analyses. Analysis will be performed under the intention-to-treat paradigm.

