The *primary analysis* of the intervention effect on ECC will be performed using the constrained longitudinal data analysis (cLDA) proposed by Liang and Zeger.(138) Repeatedly measured ECC outcome at BL, PT, and FU will be modeled as dependent variables with the baseline mean responses constrained to be the same across intervention arms due to randomization. This model is flexible in handling missing data and has been shown to provide greater power than other models when testing intervention effects and yields valid results when data are missing at random. The clustering effect of repeated measures within a subject will be accommodated using a random subject effect. Time of measurement (BL, PT, FU) and its interaction with intervention arm will be included in the model. The time of measurement is considered as a categorical variable to allow non-linear time effect. Intervention effects are captured by the significant interaction effect. Comparison of outcome measures across intervention arms at PT and FU will be estimated based on the

model using appropriate contrasts. In order to assess whether the intervention effect is affected by physical activity change, weight change, or other factor, we will examine change patterns across intervention arms. If the change pattern differs across intervention arms, that factor will be controlled by including its main effect and interaction with the intervention arm in the primary analysis for intervention effect on memory.

Exploratory Analyses. Feasibility hypotheses are 80% or greater intervention adherence and acceptability, and no serious adverse events. These will be estimated using the 95% confidence intervals. To compare safety, we will estimate the difference in rates of adverse events across the intervention arms using 95% confidence intervals. Hypotheses of improved self-reported outcomes including depression, cognition and engagement, quality of life, and IADL will be examined using the cLDA methods described immediately above.

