Mechanism Analyses. Mechanistic hypotheses are that, relative to control, intervention arm participants will have greater hippocampal volume, enhanced DMN and CEN connectivity at PT, better metabolic function, higher levels of neurotrophic growth factors, and lower levels of inflammation and oxidative stress. Hypotheses will be analyzed using cLDA. With regard to MRI, scan analysis described immediately above will be performed on targeted pre-specified ROIs and followed by spatially unbiased whole brain voxel-based analyses. Supplemental analyses will compare across scan modalities to address the relative incremental contribution of each modality (e.g. hippocampal volume) to capturing the overall neuroimaging outcome.

Moderator and Mediator Analyses. Analyses will be performed to determine the role of adherence, years of education, age, baseline cognitive scores, comorbidity, and *APOE* ε 4 carrier status (an indicator of elevated ADRD risk) in moderating intervention outcomes using cLDA. We hypothesize in particular that participants with greater adherence, more education, and lower comorbidity will experience larger ECC score gains. A three-way interaction between potential moderators, intervention arm, and time of measurement will be included in the model and a significant three-way interaction indicates the moderating effect. To evaluate hypothesized mediators of the speed training and MIND foods (e.g., inflammation, growth factors, oxidative stress, hippocampal volume), we will use the approach proposed by Krull and Mackinnon (2011) (147) that allows the testing of mediating effects in clustered data. Using the change in ECC outcome from baseline as the dependent variable, a series of three mixed effects models, as outlined by Krull and Mackinnon, will be fit and regression coefficients from these models will be used to estimate the direct and indirect treatment effects.

The cLDA provides valid inference when data are missing due to random dropouts. Sensitivity analyses will be performed to examine to what extent the results are affected when dropouts are not missing at random. Analyses based on complete cases, mean imputation, and worst case imputation will be performed. In addition, a pattern mixture model will be used to allow different intervention effects for subjects with different missing data patterns. Results based on these models will be compared to results from cLDA.

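### The primary model can be changed by post-randomisation differences between arms; its covariance structure and missing strata are lesser, cheap repairs

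*Combined protocol and SAP*

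**What the plan says.** All of this is in the combined protocol and SAP.

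- **Analytic Plan, primary analysis.** The model is a constrained longitudinal analysis (cLDA) of the executive composite (ECC) at baseline (BL), post-training (PT) and follow-up (FU), with baseline means held equal across arms. Its terms are given as "Time of measurement (BL, PT, FU) and its interaction with intervention arm will be included in the model", and for the covariance "The clustering effect of repeated measures within a subject will be accommodated using a random subject effect".
- **Same section, conditional adjustment.** The purpose is introduced with "In order to assess whether the intervention effect is affected by physical activity change, weight change, or other factor". The rule is then "If the change pattern differs across intervention arms, that factor will be controlled by including its main effect and interaction with the intervention arm". No test, threshold or closed list of factors is given. The sentence ends by naming memory as the outcome, although the primary outcome is ECC.
- **Recruitment and Randomization.** "Randomization will be stratified by age (60-69; 70 and over) and MRI completion".
- **Analytic Plan, Preliminary Analyses.** "The baseline characteristics will be compared across treatment arms and between participants who do and do not complete the study". The consequence is "If any significant differences exist, we will control for differences in the subsequent analyses". Baseline outcome scores are also compared across arms. The same paragraph commits the analysis to intention to treat.
- **Missing data, at the end of the moderator and mediator section.** "Analyses based on complete cases, mean imputation, and worst case imputation will be performed", together with a pattern mixture model. These address dropout and none of the points here.

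**The concern.** **Main point.** Activity and weight change are measured after randomisation. Every arm receives food weekly, but the foods differ between the MIND and control conditions, so an arm difference in weight change may be an effect of treatment. Adjusting for it then removes or distorts part of that effect. Once the factor-by-arm interaction is in the model, the contrast also depends on the factor value at which it is read, and the plan states none. A primary result obtained this way is not the total effect that intention to treat calls for.

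**Second.** A random subject effect with independent residuals assumes equal variances and equal correlations at the three visits. If that is wrong, the model-based standard errors at PT and FU are wrong. The Specific Aims name both visits in the primary hypotheses.

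**Third.** Leaving the stratification factors out makes the tests slightly conservative and gives up some power.

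**Minor.** Between randomised arms, significant baseline differences are chance, so chance partly picks the covariates. Testing baseline scores across arms also sits badly with a model that sets those means equal because of randomisation.

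**Working it through.** **Inputs from Power and Sample Size:** up to 50 per arm, 15% attrition (50 × 0.85 = 42.5), BL to follow-up correlation 0.7, six two-sided Bonferroni comparisons (0.05/6 = 0.0083, critical z = 2.638). With SD 1, the residual variance after baseline is 1 − 0.7² = 0.51. Everything else below is assumed.

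**The plan's own figure.** With 50 analysed per arm, SE = √(2 × 0.51/50) = 0.143 and power at 0.5 SD is Φ(0.5/0.143 − 2.638) = 80.6%, which matches the stated 80%. With 42.5 per arm, SE = 0.155 and power is 72.2% (71.1% with the t distribution). The simulations, with 42 per arm, start from about 70%.

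**1. Post-randomisation rule.** Assume both MIND food arms shift the factor by d SD, and the factor correlates r with residual ECC. The rule fires on a four-arm F test at 0.05, and the mean-centred factor and its interaction with arm are then added. When the rule fires, a food versus non-food contrast moves by about d × r × √0.51. For d = 0.5 and r = 0.3 this is 0.5 × 0.3 × 0.714 = 0.107 SD. Simulated averages over all trials, triggered or not, with a true effect of 0.5 SD:

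| Shift d | r | Rule fires | Mean estimate | Power | Rejection, no true effect |
|---|---|---|---|---|---|
| 0 | – | – | – | 71% | 0.007 |
| 0.1 | 0.3 | 8% | 0.49 | 69.6% | 0.007 |
| 0.2 | 0.3 | 15-17% | 0.48 | 67.7% | 0.009 |
| 0.3 | 0.2-0.3 | 33% | 0.48-0.47 | 65-63% | – |
| 0.5 | 0.2-0.3 | 77% | 0.44-0.41 | 54-48% | 0.014-0.022 |

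Without the rule, power is 70-71% and null rejection 0.0075-0.0094.

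**2. Random subject effect.** Let v be the pooled variance and b the pooled correlation (pooled covariance divided by v). The fitted model uses residual variance v(1 − b²). The true value at visit t is s_t² − 2b·ρ_t·s_t·s_0 + b²·s_0², where ρ_t is the correlation of visit t with baseline. The actual rejection rate is 2Φ(−2.638 × √(model/true)). Example, correlations 0.7/0.6/0.8: b = 0.7, model 0.51, true at FU 1 − 2 × 0.7 × 0.6 + 0.49 = 0.65, so the rate is 0.0194.

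| BL-PT / BL-FU / PT-FU | PT | FU |
|---|---|---|
| 0.7/0.7/0.7 | 0.0083 | 0.0083 |
| 0.7/0.65/0.7 | 0.0070 | 0.0113 |
| 0.7/0.65/0.8 | 0.0100 | 0.0159 |
| 0.7/0.6/0.8 | 0.0083 | 0.0194 |
| 0.7/0.49/0.7 | 0.0043 | 0.0203 |
| 0.7/0.6/0.85 | 0.0100 | 0.0229 |
| 0.7/0.7/0.8 | 0.0121 | 0.0121 |
| all 0.7, post-baseline SD 15% larger | 0.0117 | 0.0117 |
| all 0.7, post-baseline SD 15% smaller | 0.0053 | 0.0053 |

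Simulated REML fits (40,000 per case) agree: for 0.7/0.6/0.8 they give 0.0079 at PT and 0.0193 at FU. An unstructured covariance with Kenward-Roger degrees of freedom gave 0.0076-0.0091 in every pattern simulated.

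**3. Strata.** Suppose the strata explain R² of the residual variance. If they are omitted, the model uses 0.51 while the truth is 0.51(1 − R²); if included, both use the latter (42.5 per arm).

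| R² | Level if omitted | Power omitted | Power included |
|---|---|---|---|
| 2% | 0.0077 | 72.4% | 73.3% |
| 5% | 0.0068 | 72.7% | 75.0% |
| 10% | 0.0054 | 73.3% | 77.8% |

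If they explain nothing, t-based power goes from 71.1% to 71.0%.

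**4. Baseline trigger, between-arm part only.** With 13 independent tests at 0.05 (the number and level are assumed; the plan gives neither), the chance of at least one significant difference is 1 − 0.95¹³ = 49%. Simulated type I error at nominal 0.0083 was 0.0085 unadjusted and 0.0076 with test-selected covariates.

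**The case against.** **The shifts are hypothetical.** The documents give no expected arm difference in weight or activity, and the Interventions section builds the controls to mimic the active conditions, with the same ordering, delivery, play and incentive ceiling. This stands: at 0.1 SD almost nothing happens, and material null inflation appears only near 0.5 SD. A reader might infer that the rule generally invalidates the primary test; the documents do not support that. What survives is the change of estimand whenever treatment is the cause of the trigger.

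**Equal correlation is inferred.** The plan states a random subject effect but does not say the residuals are independent. This stands as a condition on the second point. It would also be wrong to infer that only FU is at risk: PT runs from 0.0043 to 0.0121 depending on the pattern.

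**Strata are not excluded.** The model description is silent on them, and omission errs on the safe side. This stands; the gain is modest and depends on the assumed R².

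**The baseline trigger does no measurable harm.** A reader might infer that it inflates type I error. The between-arm simulation shows that it does not. The comparison of completers with non-completers was not simulated, so nothing is claimed about it; adjusting for predictors of dropout can support the missing-at-random assumption.

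**Conclusion.** The concern holds, with unequal weight across its parts. The post-randomisation rule should leave the primary model because, when an intervention moves the factor, it replaces the intention-to-treat effect with something else. The loss runs from negligible at a 0.1 SD shift to about 16-22 power points at 0.5 SD (70% to 54-48%), given two shifted arms and a correlation of 0.2-0.3. The random subject effect, if residuals are independent, is exact under equal variances and correlations; under decay it lets the FU test run at 0.011-0.023 instead of 0.0083. Adding the strata is worth about 1 to 4.5 power points if they explain 2-10% of residual variance. The baseline trigger is a minor remark. The second and third points concern modelling choices that can be improved. They do not show that the analysis was left unspecified.

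**What to change.** - Remove the conditional adjustment for post-randomisation change from the primary model. Report it as a labelled sensitivity analysis with its factors named, and correct memory to ECC. Treatment and Adherence Modifiers places weight among the baseline measures, so state which visits supply weight change.
- Specify an unstructured 3 × 3 covariance with Kenward-Roger degrees of freedom.
- Add age stratum by time and MRI stratum by time to the primary model.
- Report baseline characteristics by arm descriptively and drop the between-arm significance trigger.

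The cost is SAP wording, with no new data. The unstructured matrix has six parameters instead of two and loses about 1 point of power if equal correlations do hold. The strata cost about 0.1 point if they explain nothing. Moving the conditional adjustment loses no information, since the adjusted result is still reported.

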Intervention Maintenance. After the 12-week post-training assessment, incentives and food deliveries will cease but participants will have continued access to BrainHQ. Those in the MIND or MINDSpeed arm will be encouraged to maintain MIND food consumption with utilization of the MINDSpeed Cookbook which details the foods and recipes used in the trial. Maintenance was chosen over total cessation of the intervention because it holds potential to maximize treatment potency, provides information on the rates of self-managed adherence (speaks to reach and effectiveness of the interventions), and should enhance subject retention. This phase of the study will provide information on the degree to which the trainings were incorporated into subjects' lifestyle in a sustainable manner. We will use intent-to-treat principles when analyzing the 6 month follow-up data. The adherence information from this phase of the study will be used in exploratory analyses. Subjects in the Food Control arms will receive the MINDSpeed Cookbook at the end of study participation.

Strategies for Treatment and Measurement Fidelity. Treatment fidelity and monitoring as defined by the NIH Behavior Change Consortium Strategies(97) and checklist(98) is enhanced by app-delivery and daily food and objective game/video data. A help call button on the app allows the participant to text research staff or request a call back (8 to 5, M-F). Staff will have access to the participant's treatment assignments. The staff on call will conduct supervised practice with the BrainHQ programs, and MIND food and food control interventions with access to our UX designer, [name], clinical nutritionist, [name], and training expert, [name] and, if needed, [name]. The staff will complete a 3-step certification process prior to working with enrolled subjects including: written test (passing score of 80%), individual module check out, and proctored mock counseling sessions with older adults using structured performance rating forms to judge quality. After certification, ongoing quality assurance checks will include observed counseling sessions once per month for first 1 month and every 3 months thereafter. A similar program of training, certification, and ongoing quality will occur for the Assessor, who will be blinded to treatment.

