Safety. We have outlined our protocols for identifying and responding to events and injuries in the Protection of Human Subjects section of the proposal (see Adequacy of Protection Against Risk). We have described standard regulatory reporting procedures in the Data and Safety Monitoring Plan (DSMP) and the operation of our Data Safety and Monitoring Board (DSMB). Cognitive training is relatively safe but anxiety and burden can occur and will be monitored. MRI is a safe procedure for people who do not have metal implants or other contraindications. Study personnel will screen participants for these risk factors prior to enrollment. Before

entering the MRI environment, participants will be re-screened for MRI contraindications per IU standards. Physical confinement or noise in MRI can be uncomfortable. All efforts are made to assure participant's comfort. Blood draws will be conducted by trained and certified staff. Finally, a small number of participants may develop depression, dementia, or physical dysfunction during the study. Should this occur, we will direct the subject to appropriate clinical care (i.e., PCP or specialty clinic as needed). We will also direct subjects to appropriate clinical care based on blood pressure and pulse values obtained during Baseline, Post-Training, or Follow-Up appointments in clinic. This is not a study procedure, but rather a process for addressing potential safety issues within the hospital environment.

Measures. All assessments will be completed by a trained, certified, and blinded Assessor; all data will be entered into Research Electronic Data Capture (REDCap). We have decades of experience completing assessments with older adult participants.

Unless otherwise noted, measures are taken at baseline (BL), immediate post-training (PT), and 6 month follow-up (FU). BL, PT and FU assessments may be conducted at Eskenazi, IU Health Neuroscience Center, participant's homes, or via telephone with abbreviated outcome measures as necessary. [During the COVID-19 health crisis, all study visits will be completed by phone or Zoom, and biospecimen collection, imaging, and Viromeaging substudy enrollment will cease.]

"Off-line" training is tracked via subject-report at PT and FU of all non-study training, either cognitive or physical. Participants will indicate frequency and duration of leisure cognitive, physical, and formal educational activities.(99)

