VBM grey matter density (GMD) images, DTI FA and MD images, task-related contrast images, RS-fcMRI component maps, and ASL CBF images will be compared between those receiving the combined intervention, a single intervention, and control cross-sectionally and longitudinally on voxel-wise and ROI levels. Cross-sectional voxel-wise analyses will compare the scans between groups at BL, PT, and FU. Longitudinal voxel-wise analysis will model time-by-group interactions using a two-way Analysis of Covariance (ANCOVA) model. All voxel-wise analyses will be performed in SPM8 (or SPM12). For regional analysis, we will extract a mean value for ROIs from the final stage preprocessed scans. Specifically, cross-sectional and longitudinal change in regional brain atrophy (i.e., MTL, frontal lobe), WM integrity (i.e., FA, MD from MTL WM tracts), task-related fMRI activation (i.e., activation from task-specific regions), resting-state connectivity (e.g., DMN connectivity from medial parietal lobe and MTL, etc.), and cerebral perfusion (i.e., whole brain, frontal lobe, etc.) will be compared between groups using values extracted from hypothesized target ROIs (see Analytic Plan).

Cost. We will track all personnel, equipment, technology, and support costs associated with delivering the interventions thus allowing an estimation of intervention costs on a per subject basis.

Power and Sample Size. The primary analysis of the study focuses on the evaluation of the effectiveness of the interventions on the cognitive outcome, ECC. We therefore determined the sample size to ensure adequate power for this analysis. In these prior studies, speed of processing training was found to have an effect size (ES) of 1.4 standard deviation (SD) at immediate post-training (PT) and 1.2 SD at one year PT on processing speed outcomes.(22) MIND diet is a brain health optimized hybrid of the Mediterranean-DASH diets, and the latter were found to have an effect size of 0.44 to 0.56 SD on executive function and speed of processing(136). There are no published trials of speed of processing training combined with MIND diet but we expect a large effect size of the combined intervention. With an overall alpha level of 0.05 for six Bonferroni-

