adjusted two-sided comparisons, a conservative estimate of the correlation of 0.7 between baseline and followup based on prior studies, and 15% attrition rate (in our recent GRACE trial of 951 older adults—62% had < 12yrs of education—91% completed the 6-month follow-up assessment)(73), the sample size of up to 50 participants per treatment arm will yield 80% power to detect an effect size of >0.5 SD based on the constrained longitudinal data analysis (cLDA).(137) The cLDA (138) has been shown to produce greater efficiency and handle missing data more flexibly with valid inference when data are missing at random.(137, 139). Cognitive aging studies support an effect size of over one-half standard deviation as clinically meaningful.(140-142)

Exploratory Aims and Power: Outcomes include inflammation, metabolic function, oxidative stress, and hippocampal structure and function (via MRI). For non-imaging outcomes, we will have a full sample and adequate power to detect effect sizes of 0.6. Imaging creates anxiety and discomfort for some, however. Thus, in addition to using information and communication strategies shown to reduce imaging anxiety(143) we will complete imaging on the minimum necessary. From the literature, we anticipate large effect sizes on the brain outcomes of hippocampal structure and function. Cognitive training has resulted in changes in brain structure with approximate effect size of 0.56 in left hippocampus volume following spatial navigation training among healthy younger and older men(144) and an approximate effect size of 0.47 in gray matter density (GMD) after the completion of a multidomain computerized cognitive training among healthy older adults.(20) In addition, our preliminary results showed an effect size of 0.5 in annual percent change in hippocampal volume and 0.8 in annual percent change in hippocampal GMD among older adults without MCI who are frequently engaged in reading and puzzle-solving compared to those who are not. Food interventions alone have had an effect size of 0.7 on hippocampal volume.(9, 56) Other studies support effect sizes of 0.64 to above 1.00 on functional connectivity.(145, 146) A one-half subsample of each arm (n=22 per arm) with an alpha level of 0.05 and a correlation of 0.7 between baseline and post-training provides 80% power to detect an effect size of 0.7 or larger for the brain imaging outcome.

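### Adding post-randomisation change in activity, weight or another factor to the primary ECC model can replace the total effect of assignment with a different quantity

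*Combined protocol and SAP*

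**What the plan says.** The primary-analysis paragraph of the Analytic Plan models the ECC at baseline, post-training (PT) and six-month follow-up (FU) by cLDA. The arms share one baseline mean, and intervention effects are read from arm-by-time contrasts. The paragraph then asks whether the effect is influenced by change in physical activity, change in weight, or some other factor that it does not name. Its instruction is: "If the change pattern differs across intervention arms, that factor will be controlled by including its main effect and interaction with the intervention arm". The rest of that sentence places the adjustment in the primary analysis. It also names the outcome as memory, although Cognitive Outcome Measures defines the primary outcome as the ECC.

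Other sections bear on this:

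- Preliminary Analyses: "Analysis will be performed under the intention-to-treat paradigm". Intervention Maintenance: "We will use intent-to-treat principles when analyzing the 6 month follow-up data".
- Measures: off-line "training is tracked via subject-report at PT and FU of all non-study training, either cognitive or physical". Physical activity therefore has a stated post-baseline source. Weight is listed only among the baseline measures, under Treatment and Adherence Modifiers.
- Moderator and Mediator Analyses already contains exploratory models for direct and indirect effects. The sensitivity analyses described there concern missing data only.

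No section keeps the contrast without the factor as primary or asks for it alongside. None gives the criterion for a difference between arms, the list of factors, their coding, or the factor value at which the contrast is to be read.

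**The concern.** The rule selects a variable measured under treatment because it differs by assigned arm, and then conditions on it. The difference may be chance, but it may also be an effect of the arm. If it is an effect, three things follow.

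- The adjusted contrast drops whatever part of the ECC effect passes through the factor.
- If the factor and cognition share an unmeasured cause, conditioning on the factor opens a biasing path, even when the factor itself does nothing to cognition.
- With a factor-by-arm interaction there is no single arm effect. The result depends on the factor value chosen, and the plan does not state one.

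Participants would still be analysed in the arm to which they were randomised, but the contrast would not be the total effect of assignment. The headline estimate could move in either direction, and the error rate could exceed the planned 0.05/6 per comparison. The open-ended factor list also means that the primary model could be settled after post-randomisation data have been seen.

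**Working it through.** **1. The plan's own figure.** Power and Sample Size gives the inputs: "With an overall alpha level of 0.05 for six Bonferroni" and "adjusted two-sided comparisons, a conservative estimate of the correlation of 0.7 between baseline and followup based on prior studies, and 15% attrition rate"; it concludes that "the sample size of up to 50 participants per treatment arm will yield 80% power to detect an effect size of >0.5 SD". The baseline-adjusted SD is √(1 − 0.7²) = 0.714 and alpha per comparison is 0.05/6 = 0.00833. Then

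n = 2 × 0.51 × (2.638 + 0.842)² / 0.5² = 49.4, so 50 per arm, with 80.6% power.

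The figure reproduces if 50 is the number analysed. After 15% loss (42.5 per arm), power at 0.5 SD is 72.2% and the effect detectable with 80% power is 0.714 × √(2/42.5) × 3.480 = 0.54 SD, which still fits the plan's wording. The point below does not depend on this.

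**2. What the adjustment does to the contrast.** Let *a* be the arm's effect on the factor (in SD) and *b* the factor's slope on ECC (SD per SD). With the factor coded as change and centred, the adjusted contrast is total − *b* × *a*. For a true 0.50, *b* = 0.3 and *a* = +0.5, this is 0.50 − 0.15 = 0.35; for *a* = −0.5 it is 0.65.

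**3. The rule as a whole.** Two-arm simulation with 43 per arm, correlation 0.7 and alpha 0.05/6. The factor and its arm interaction are added only if the arms differ on the factor at p < 0.05. That threshold and all values of *a* and *b* are assumptions, because the documents give none. 8,000 replicates per case, true effect 0.50 SD:

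| Shift *a* | Slope *b* | Estimate when added | Averaged over the rule | Power: rule / no factor |
|---|---|---|---|---|
| +0.5 | 0.3 | 0.35 | 0.38 | 45% / 70% |
| −0.5 | 0.3 | 0.65 | 0.62 | 91% / 71% |
| 0 | 0.3 | 0.50 | 0.50 | 71% / 70% |
| +0.2 | 0.2 | 0.46 | 0.48 | 66% / about 70% |
| −0.2 | 0.2 | 0.54 | 0.52 | 74% / about 70% |

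In the first row the rule triggers in 62% of trials. The average is below a simple mix of 0.35 and 0.50 because the untriggered trials are those with a small observed shift. Their mean estimate is (0.38 − 0.62 × 0.35)/0.38 = 0.43.

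**4. Error rate with no true effect.** Assume a shared cause explains 30% of both the factor and the ECC residual. The slope it induces is 0.30 × 0.714 = 0.21, so a 0.8 SD shift biases the adjusted contrast by −0.8 × 0.21 = −0.17 SD. Rejection under the rule is 5.5% at a 0.8 SD shift, 1.8% at 0.5 SD and 0.8% at 0.2 SD, against 0.83% planned. Repeat simulations gave 5.1% to 5.6%, up to 2.1%, and up to 0.9%.

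**5. Coding.** A three-visit cLDA with the factor as post-baseline change gives the same estimates (0.35 when added, 0.38 over the rule). With a time-fixed factor and no time interaction, the estimates for a true 0.50 are 0.47 (shift +0.5), 0.53 (shift −0.5) and 0.49 (shift +0.2). Under no true effect the estimate is −0.02 at a 0.8 SD shift.

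**6. Reading point.** With slopes *b0* = 0.2 (control) and *b1* = 0.4 (active), *a* = 0.5 and control-arm mean 0, the contrast at factor value *m* is

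total − *b1* × *a* + (*b1* − *b0*) × *m* = 0.50 − 0.20 + 0.2*m*.

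This is 0.30 at the control-arm mean (*m* = 0), 0.35 at the pooled mean (*m* = 0.25) and 0.40 at the active-arm mean (*m* = 0.5).

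**7. Chance triggering.** If *k* independent factors are each tested at 0.05 and no arm affects any of them, at least one enters the model with probability 1 − 0.95^*k*: 9.8%, 14.3% and 22.6% for *k* = 2, 3 and 5.

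**The case against.** The best defence is that the effect may be small.

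- **Coding.** The plan names a main effect and an arm interaction for the factor but no time interaction, whereas its moderator section writes out a three-way term when it wants one. A literal reading is therefore a time-fixed change score, for which a true 0.50 becomes 0.47 or 0.53. On a normal approximation, a bias of 0.02 lifts rejection only from 0.83% to 0.89%, and an estimate of 0.47 has 66% power against 73%.
- **Size of the shift.** The interventions are app-based games and delivered foods, and the controls are built to resemble them. Nothing in the documents suggests an arm effect of 0.5 to 0.8 SD on physical activity.
- **Weight.** No post-baseline weight measurement is stated, so that trigger may not be usable.
- **Intent.** The passage opens as if it were a check on robustness.

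The first three points stand as limits on size. They do not rescue the rule: the coding is unstated, the factor list is open, and the plan gives no ground for ruling out either reading. The fourth fails on the text, because the adjustment is placed in the primary analysis and no unadjusted contrast is kept beside it.

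**Conclusion.** The rule is wrong as written and should be changed before analysis. If it triggers on a factor that the arms really change, and that factor is related to ECC, the primary contrast stops estimating the total effect of assignment.

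The size is conditional and rests on assumed inputs. It is zero if the arms do not affect the factor or if the factor is unrelated to ECC given arm. It is about 0.02 SD over the rule for a 0.2 SD shift with slope 0.2. For a 0.5 SD shift with slope 0.3 it is about 0.03 SD under time-fixed coding, and 0.15 SD (0.12 averaged over the rule) under change coding. Material inflation of the error rate appeared only under change coding, with shifts of 0.5 SD or more and a substantial shared cause. Priority is high because the rule acts on the primary estimate, the intention-to-treat statements point the other way, and nothing else in the plan recovers the unadjusted result.

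**What to change.** - Delete the rule from the primary-analysis paragraph. State that the cLDA without post-randomisation covariates is the only primary ECC analysis at PT and FU.
- Move any model adjusted for change in physical activity or weight to the exploratory mediation or sensitivity analyses. For each, state the factor, its coding, the value at which the contrast is read, and the assumption of no unmeasured common cause of factor and outcome.
- Two minor corrections to make at the same time: name the ECC in place of memory in that sentence; and, where the plan says "Analyses will be performed to determine the role of adherence, years of education, age, baseline cognitive scores, comorbidity", describe the adherence term as an exploratory association. Adherence arises after randomisation and refers to different activities in different arms, so its interaction does not show effect modification.

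The cost is SAP wording only. No new data or estimator is needed, and the planned power calculation is unchanged.
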